5.4.4 Analysis of Efficacy Parameters

Response Rate

ORR is defined as the proportion of subjects who achieve a CR or partial response (remission) (see [Section 4.2](#)). ORR will be calculated, and the corresponding 2-sided exact 95% CI will be derived.

Duration of Response

For subjects who achieve objective response, DOR is defined as the time from the first tumor assessment showing response to the time of confirmed disease progression or death due to any cause, whichever occurs first. Subjects who are still alive and free from progression at the time of data cutoff date, are lost to follow-up, have discontinued from the study, or have initiated other non-protocol antitumor therapy (NPT) will be

censored at the last evaluable tumor assessment. A Kaplan-Meier (K-M) curve will be presented for DOR and K-M median will be calculated with 2-sided 95% CI.

Progression-Free Survival

PFS is defined as the time from first dose to documented disease progression, or death from any cause, whichever occurs first. Subjects who are still alive and free from progression at the time of data cutoff date, are lost to follow-up, have discontinued from the study, or have initiated NPT will have their PFS time censored at last evaluable assessment (or, if there is no post-baseline tumor assessment, at the time of first dose). A K-M curve will be presented, and K-M estimates as well as exact 2-sided 95% CIs will be calculated for event time quartiles, and event-free rates at the protocol-specified disease assessment times.

6-month and [CCI] Progression-Free Survival Rates

PFS-6 rate is defined as the K-M estimate of subjects alive and without documented disease progression at 6 months. In this study, 1 month is defined as 30.4375 days. The K-M method will be used to estimate the PFS-6 rate and corresponding 95% CIs.

[CCI]

Overall Survival

Overall survival (OS) is defined as the time from first dose to death from any cause. Subjects who are still alive at the time of data cutoff date, are lost to follow-up, or have discontinued from the study will have their OS time censored at the last date known to be alive on or before the data cutoff date. The analysis of OS will be conducted, where applicable, using the same analysis method described for PFS.

The SAP will describe analyses of all other exploratory endpoints.

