#### **10.7.4 Overall Survival**

Overall survival is defined as the time from date of enrollment until date of death due to any cause. Subjects who are known to be alive or whose survival status is unknown will be censored at the date last known to be alive. Subjects who lost to follow-up for survival immediately after randomization will be censored at first dose date.

OS will be summarized for safety analysis set. The analysis methods for OS will be similar to those described for progression-free survival. Censoring rules are defined in more detail in [Appendix 12.4](#).

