## **12.2 Imputation rules for partial or missing dates**

Imputation of partial dates will be made for AE onset and stop dates, start and end dates of concomitant medication, start date of subsequent anticancer therapy, date of initial diagnosis and death date. If dates are completely missing, no imputation will be made. For any partial date with missing year, no imputation will be made.

The general rule for imputation is:

- If only day is missing, then the 15th of the month will be used.
- If only year is present, then June 30th will be used.

If such imputation date for initial diagnosis is on or after date of first dose, then date of first dose – 1 will be used. If such imputed date for subsequent anticancer therapies is before date of last dose, then date of last dose + 1 will be used.

If the imputed date is for an AE start date and is in the same year and month as but before the first dose date, then the first dose date will be used, or if the imputed AE start date is after the AE end date, then the AE end date will be used. If the imputed date is for an AE start date and is in the same year and month as but after the last dose date + 30 days, then the last dose date + 30 days will be used.

If the imputed date is for an AE end date and is after the death date, then the death date will be used, or if the imputed AE end date is before the AE start date, then the AE start date will be used.

Every effort will be made to obtain complete dates for deaths. If both month and day are missing for death date or a death date is totally missing, do not impute and censor the subject survival time. If death year and month are available but day is missing, the following algorithm will be used:

- If mmyyyy for last contact date = mmyyyy for death date, set death date to the day after the last contact date.
- If mmyyyy for last contact date < mmyyyy for death date, set death date to the first day of the death month.
- If mmyyyy for last contact date > mmyyyy for death date, data error and do not impute.

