#### 12.4 Overall survival censoring rules

Situation	Date Death or Censoring	Outcome
Death at any timepoint	Date of death	Death
Lost to follow-up immediately after 1st dose of study drug	Date of 1st dose study drug	Censored
Not known to have died at or after the analysis cutoff date	The date last known alive before data analysis cutoff	Censored
Known to have died after the analysis cutoff date	Date of data analysis cutoff	Censored

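### SAP 12.2 censors subjects known to be dead when the death month or the whole date is missing, which conflicts with SAP 10.7.4 and raises overall survival on average

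*SAP*

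**What the plan says.** SAP 12.2 opens by listing the partial dates to be imputed, among them "date of initial diagnosis and death date". It adds that completely missing dates are not imputed. Its general rule for a date with only the year reads "If only year is present, then June 30".

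The same section then gives a rule specific to deaths. It promises every effort to obtain complete death dates. If "both month and day are missing for death date or a death date is totally missing", the instruction is "do not impute and censor the subject survival time". No censoring date is given. If only the day is missing, the death remains an event, dated at the day after last contact or the first of the death month, depending on when last contact fell.

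Three other places define who is an OS event and who is censored:

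- SAP 10.7.4 defines OS as "time from date of enrollment until date of death due to any cause" and states the censoring rule: "Subjects who are known to be alive or whose survival status is unknown will be censored at the date last known to be alive".
- The SAP 12.4 table gives "Death at any timepoint" the outcome Death, dated at the date of death. Its last row censors, at the cutoff, deaths known to have occurred after the analysis cutoff.
- Protocol 5.4.4 censors "Subjects who are still alive at the time of data cutoff date, are lost to follow-up, or have discontinued from the study".

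**The concern.** A subject whose death is established but poorly dated is analysed as a censored survivor. Kaplan-Meier estimation assumes that a censored subject has the same future risk as those still followed. Here the subject is censored because death has already occurred, so the assumption fails and the curve tends to be too high from the true death time onward.

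OS is a secondary objective, reported by cohort in 15 subjects (200 mg BID) and 9 subjects (400 mg QD). At those sizes one recoded death can move a median. Long-term survival follow-up is by clinic visit or telephone about every 12 weeks (Protocol 4.4.2), so an incompletely dated death is possible. Because 12.2 sets no censoring date and conflicts with 10.7.4, two programmers following the SAP could also produce different OS results.

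**Working it through.** **1. The rules side by side, for a subject known to have died by the cutoff**

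| Death date recorded | 12.2 general rule | 12.2 death rule | 10.7.4 | 12.4 death row |
|---|---|---|---|---|
| Day missing | 15th of month | Event, dated from last contact | Not in the censored group | Event |
| Year only | June 30 | Censor, date not stated | Not in the censored group | Event, needs a date |
| Wholly missing | No imputation | Censor, date not stated | Not in the censored group | Event, needs a date |

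For a year-only death, 12.2 conflicts with itself unless the death rule is read as overriding the general one. For a wholly missing date, the two parts of 12.2 agree on not imputing. The conflict is then between censoring and the event definitions in 10.7.4, 12.4 and Protocol 5.4.4. A known death is neither alive nor of unknown status.

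**2. Direction of the effect: a fixed example**

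The documents give no expected OS median or event count, so there is no stated figure to reproduce. Take 15 subjects who die at months 1, 2, …, 15. Twelve weeks is 84 / 30.4375 = 2.76 months. Censor the month-8 death at 8 − 2.76 = 5.24 months.

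- True dates: S(6) = 9/15 = 0.600; S(9) = 6/15 = 0.400; S(8) = 7/15 = 0.467, so the median is 8.
- Censored: after month 5, S = 10/15, and 9 subjects remain at risk at month 6.
  - S(6) = (10/15)(8/9) = 0.593.
  - S(7) = (10/15)(7/9) = 0.519, with no event at month 8.
  - S(9) = (10/15)(6/9) = 0.444, so the median is 9.

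The curve is slightly lower before the true death time and higher after it.

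**3. Typical size**

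Assumptions, none of them in the documents: exponential survival, every subject followed to death, and 0, 1 or 2 randomly chosen deaths recoded as censored at a last contact uniform over the preceding 2.76 months. There were 20,000 simulated trials per setting. The table shows the middle value of the estimated K-M medians, in months.

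| n | Assumed median | None censored | One censored | Two censored |
|---|---|---|---|---|
| 15 | 9 | 9.0 | 9.6 | about 10.2 |
| 15 | 6 | 6.0 | 6.4 | 6.7 to 6.8 |
| 9 | 9 | 9.0 | 10.0 | about 11.0 |

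The ranges reflect simulation error between runs. With n = 15 and median 9, one recoded death left the K-M median unchanged in about 62% of trials. The 95% sampling range of the median itself was about 4.0 to 17.2 months.

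**4. A second set of assumptions**

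This set used a 24-month cutoff, last contact at the preceding fixed 12-week contact, assumed medians of 6, 9 or 12 months, and 4,000 trials per setting. For n = 15, mean K-M survival between 6 and 12 months rose by 2.0 to 2.9 percentage points with one recoded death and by 4.2 to 6.0 with two. The mean shift was upward in every setting, for n = 15 and n = 24. In 0.6% to 3.0% of single trials the 12-month estimate was lower.

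**5. Does keeping the deaths as events repair it?**

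Under step 3 (n = 15, median 9, one death), an event dated at last contact plus one day gives a typical median of 8.9, against 9.0 with true dates and 9.6 under the SAP rule. Under step 4, with one to three such deaths, that earliest date lowers survival at 6 to 12 months by 0.2 to 2.5 points.

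**The case against.** The best defence is that 12.2 is a specific rule that completes the general ones. The 12.4 death row assigns the date of death, so it cannot be applied without one, and 12.2 also departs from its own general rule when only the day is missing. This narrows the conflict with 12.4 and the June 30 conflict. It does not remove the conflict with 10.7.4, which states who is censored and mentions no exception, and it does not make the censoring non-informative.

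The trigger is also narrow. Contact about every 12 weeks would usually bracket a death to within about three months, the SAP has a death information form for all deaths, and it commits to seeking complete dates. No document reports a single affected death. All of this stands: the effect may be zero.

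Protocol 5.3 allows date imputation only for adverse events and concomitant medication, so not imputing agrees with the protocol. But the SAP already dates deaths with a missing day, and declining to impute does not require calling a dead subject a survivor.

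A reader might infer that every such death raises the curve. The example in step 2 shows otherwise: the upward shift is an average, and it applies from the true death time onward. A reader might also infer that deaths are hidden or a study decision affected. The documents do not support that: SAP 10.6.1 reports all deaths with their cause, SAP 5 tests no hypothesis, and the decision not to start Phase 2 followed response-rate criteria (SAP 3.1).

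**Conclusion.** The rule is wrong as written, and the correction is minor. SAP 12.2 removes known deaths from the OS event count in a case that 10.7.4 and Protocol 5.4.4 do not allow for. It conflicts with the 12.4 death row, leaves a year-only death with two instructions, and sets no censoring date.

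The bias is upward on average. For 15 subjects and an assumed 9-month median it is about 0.6 months on the typical median for one affected death and about 1.2 for two. For an assumed 6-month median it is about 0.4 and 0.7 to 0.8. These figures rest on exponential survival and a last contact within 12 weeks of death, and they are small beside the sampling error of a median in 15 subjects. With no affected deaths there is no bias, and the documents do not say how many there are.

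**What to change.** Replace the censoring sentence in SAP 12.2 with a rule along these lines:

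- Count every death known to have occurred on or before the analysis cutoff as an OS event.
- If only the year is known, date it at the later of January 1 of that year and the day after the subject was last known alive.
- If the date is wholly missing but the death was reported by the cutoff, use the day after last known alive.
- Leave the 12.4 row for deaths after the cutoff unchanged.
- State that this overrides the June 30 rule, and refer to it from 10.7.4 and 12.4.

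Add a sensitivity analysis that dates these deaths at the latest compatible date: the earliest of the end of the known year, the date the death was reported, and the cutoff. Report how many deaths were dated this way. The branch of 12.2 for a last contact after the death month, treated as a data error with no imputation, also needs a stated OS outcome.

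The cost is a few lines of SAP text and no new data. The reported OS may be slightly less favourable. The earliest-date rule leans slightly low, which is why the latest-date analysis should accompany it.

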### 12.3 PFS events and censoring rules

Here PFS is the primary analysis that only includes well-documented and verified progression events.

Same rules are used for DOR identify progression or censoring date.

Situation	PFS	
	Date of Progression or Censoring	Outcome
Progression documented on scheduled visit	Date of scheduled visit	Progression
Progression documented between scheduled visits	Date of unscheduled visit	Progression
Treatment discontinuation for undocumented progression	Date of last visit with adequate assessment	Censor
Death before first PD assessment	Date of death	Progression
Death between adequate assessment visits	Date of death	Progression
Death or progression after only one missed visit	Date of death	Progression
Death or progression after 2 or more missed visits	Date of last visit with adequate assessment	Censor
Death or progression after 2 or more missed visits and only baseline tumor assessment available	Date of 1st dose of study drug	Censor
No baseline tumor assessments	Date of 1st dose of study drug	Censor
Baseline tumor assessments only and no evidence of documented PD, treatment discontinuation due to PD or death within no more than one missed visit	Date of 1st dose of study drug	Censor
No progression	Date of last visit with adequate assessment	Censor
Treatment discontinuation for toxicity or other reason	Date of last visit with adequate assessment	Censor
New anticancer treatment started	Date of last visit with adequate assessment	Censor

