3.10 WITHDRAWAL OF SUBJECTS FROM STUDY TREATMENT

The investigator, in consultation with the medical monitor, may withdraw any subject from study treatment, if, in the investigator's opinion, it is not in the subject's best interest to continue.

Any subject has the right to withdraw from the study treatment at any time. In addition, subjects may be withdrawn from study treatment for the following reasons:

- Progressive disease
- Start of alternative anticancer therapy
- Adverse event
- Pregnancy
- Investigator decision
- Subject's withdrawal of consent from study
- Decision by sponsor to terminate the study
- Subject lost to follow-up
- Death
- Other

Note: If the effects of ACP-196 stimulate an immune response in the tumor, it is possible that there could be pseudoprogression. If there is uncertainty regarding whether there is true cancer progression, the subject may continue study treatment and remain under close observation (e.g., evaluated at 4-week intervals) pending confirmation of progression. In particular, transient worsening of disease early in therapy or during temporary interruption of study therapy (e.g., for drug-related toxicity, surgery, or intercurrent illness) may not indicate cancer progression. In such circumstances, and if medically appropriate, subjects may resume therapy and relevant clinical, laboratory, and/or radiographic assessment can be attempted to document whether tumor control can be maintained or whether cancer progression has occurred.

Subjects who discontinue study treatment will continue to be followed on study for follow-up of safety ([Section 4.3](#)), disease progression, and survival unless they withdraw consent for further follow-up. Thus, all subjects receiving ≥ 1 dose of study drug will be followed during the immediate post-therapy and long-term follow-up assessments unless the subject withdraws consent for such follow-up to be conducted. The date the subject is withdrawn from study treatment or from the study (including long-term follow-up) and the reason for discontinuation will be recorded and also should be described on the appropriate eCRF.

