4.4 FOLLOW-UP FOR PROGRESSION AND SURVIVAL

4.4.1 Post-Treatment Disease Follow-Up

Each subject should be followed until disease progression or the start of alternative anticancer therapy. If neither of these has occurred at the time of the 30-day SFU visit, Post-Treatment Disease Follow-Up visits should occur approximately every 3 months (12 weeks) from the date of last dose until disease progression or next anticancer treatment. During this period, subjects will be followed via MRIs per investigator discretion.

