### **10.7.3 Progression-free Survival Per RANO criteria**

Progression-free survival is defined as the interval from the start of therapy to the earlier of the first documentation of objective disease progression or death from any cause,

whichever occurs first. Kaplan-Meier (K-M) methods will be used to estimate the event-free curves and corresponding quantiles (including the median).

Data from surviving, non-progressing subjects will be censored at the date of the last adequate disease assessment that is on or before the start date of the new antitumor therapy. Data from subjects who have disease progression or die after more than one missed visit will be censored at the last visit date prior to the missing assessments which lack objective disease assessment. The details of definition of progression events and censoring rules are listed in [Appendix 12.3](#).

In the primary analysis using safety analysis set, study treatment end date will be used as the date of progression for subjects who discontinued study treatment due to disease progression or death prior to 1st radiographic assessment. Data for subjects who discontinued study treatment prior to 1st radiographic assessment due to reasons other than disease progression or death will be censored at their study treatment start date.

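### SAP 10.7.3 and 12.3 give PFS event and censoring rules that conflict, or misdate events if followed literally, and state no order of precedence

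*SAP*

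**What the plan says.** SAP 10.7.3 defines PFS from start of therapy to first objective progression or death. Its general rule censors subjects who are alive and have not progressed at their last adequate assessment. For the primary analysis it then adds two rules for subjects who stop before the first radiographic assessment:

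- Stops for progression or death: "study treatment end date will be used as the date of progression for subjects who discontinued study treatment due to disease progression or death".
- Other stops: data for subjects who stopped "due to reasons other than disease progression or death will be censored at their study treatment start date".

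SAP 12.3 gives a table, also described as the primary PFS analysis. Its relevant rows are:

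- "Death before first PD assessment": event, dated at death.
- "Baseline tumor assessments only and no evidence of documented PD, treatment discontinuation due to PD or death within no more than one missed visit": censored at first dose.
- Death or progression after a single missed visit: event, with date of death as the only date given.
- "Treatment discontinuation for toxicity or other reason": censored at the last visit with adequate assessment.

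The same table is applied to DOR. Neither section says which rule prevails when two apply.

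Protocol 5.4.4 counts documented progression or death from any cause. Event-free subjects at data cutoff, and those who "are lost to follow-up, have discontinued from the study, or have initiated NPT will have their PFS time censored at last evaluable assessment" (or at first dose if there is none), are censored. Stopping treatment is not a censoring reason there. Protocol 3.10 states that "Subjects who discontinue study treatment will continue to be followed on study for follow-up of safety", disease progression and survival, and protocol 4.4.1 that "Each subject should be followed until disease progression or the start of alternative anticancer therapy".

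**The concern.** A table of PFS rules should give each subject one outcome and one date. Here some subjects fit two rules with different outcomes, and one row gives a date that cannot be right for half of the events it covers. Two programmers working from the same SAP could derive different PFS, PFS-6 and PFS-4 from the same data, and both could claim to have followed it. Because treatment stop does not end follow-up, a progression or death after the stop can be observed, so the overlap is not merely theoretical.

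The rules that apply after the first scan also reach DOR. The pre-first-scan conflicts do not, because a responder has had a scan.

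**Working it through.** The documents state no PFS rate or precision, so there is no plan figure to reproduce. The check is a comparison of the rules, followed by a small illustration on assumed data.

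**Comparison**

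| Situation | SAP 10.7.3 | SAP 12.3 | Protocol 5.4.4 |
|---|---|---|---|
| 1. Stops before first scan for another reason, then dies | Censored at treatment start, no exception stated | Event at death; the baseline-only row also withholds censoring for a death within one missed visit | Event |
| 2. Treatment ended by death before first scan | Event at treatment end | Event at death | Event (death) |
| 3. Progression after one missed visit | First documented progression | Event row, only a death date given | Event at documented progression |
| 4. Stops for toxicity or another reason after a scan, later progresses or dies | General rule censors only those alive and progression-free | Fits both the toxicity/other-reason censor row and an event row | Event, unless a listed censoring reason comes first |

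Situations 1 and 2 are contradictions between the two SAP sections. Situation 3 is an error within one row. Situation 4 is an overlap whose likely meaning can be inferred but is not written.

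**Illustration (assumed data)**

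Inputs from the documents: 15 subjects in Cohort 1 (SAP 3.2); scans at weeks 8, 12, 20 and 28 (protocol Appendix 1: Day 1 of Cycles 3, 4, 6 and 8, with 4-week cycles); 1 month = 30.4375 days. Six months is 6 × 30.4375 = 182.625 days = 26.09 weeks; four months is 121.75 days = 17.39 weeks.

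Assumed outcomes: 8 subjects progress at week 8, 2 at week 12 and 2 at week 20; 2 are progression-free and censored at week 28; one further subject varies. The estimator is Kaplan-Meier, S(t) = product of (1 − d/n) over event times up to t.

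*Situation 1. Stops for toxicity in week 5, dies in week 7.*
- Event at week 7 (12.3, 5.4.4): PFS-6 = 2/15 = 13.3%; PFS-4 = 4/15 = 26.7%.
- Censored at treatment start (10.7.3): PFS-6 = 2/14 = 14.3%; PFS-4 = 4/14 = 28.6%.

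*Situation 2. Last dose in week 5, death in week 6.* Both dates precede the first scan, so PFS-6 is 13.3% and PFS-4 is 26.7% either way. Only the event time moves.

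*Situation 3.* Not given a number. A progression dated at a later death lengthens PFS by the gap between the two; a subject who progresses and is still alive has no date in that row.

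*Situation 4. Stops for toxicity after the week-12 scan, progression on MRI at week 24.*
- Event at week 24: PFS-6 = 2/15 = 13.3%.
- Censored at week 12: 7/15 after week 8; × 5/7 = 5/15 after week 12; 4 remain at risk at week 20 with 2 events, so PFS-6 = 5/15 × 2/4 = 16.7%. PFS-4 is 5/15 = 33.3% under both readings.

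For scale, the exact (Clopper-Pearson) 95% CI for 2/15 is 1.7% to 40.5%.

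**The case against.** The strongest reply is that 10.7.3 opens its censoring rules with subjects who are alive and have not progressed, and that everything after it, including the toxicity row in 12.3, should be read under that limit. Protocol 5.4.4 similarly censors at first dose the event-free subjects who have no post-baseline assessment, so the last sentence of 10.7.3 may be meant only to apply that clause. This largely stands for the toxicity row: the benign reading is the more natural one, and under it nothing changes. It is weaker for the pre-first-scan sentence, which defines its group by timing and reason for stopping and is not tied to the earlier limit. It does not touch the two different dates for a death.

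On the one-missed-visit row, a programmer could take the progression date from the first two rows of 12.3. That is sensible, but it means overriding the row that describes the case.

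A reader might go further and infer the following, which the documents do not support:

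- *That 12.3 censors every progression seen after a toxicity stop.* The general rule in 10.7.3 points the other way.
- *That stops for progression before the first scan are in conflict.* The undocumented-progression row could be read as censoring them, but the baseline-only row exempts stops due to progression, in line with 10.7.3.
- *That censoring undocumented progression, or events after two or more missed visits, is an error.* The SAP limits progression to objective, documented events, and text and table agree on the missed-visit rule. These are conventional choices that add to protocol 5.4.4.

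The SAP cites protocol Amendment 2.0, while the protocol supplied contains later text. Departures from 5.4.4 are therefore shown against the supplied version only; the conflicts inside the SAP do not depend on it.

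**Conclusion.** The point holds as a drafting fault that should be fixed. There are two contradictions between sections that both claim the primary analysis, one row with the wrong date for progression, and one censoring row missing a qualifier, with no precedence to settle them.

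The reach is limited. PFS, PFS-6 and DOR are secondary objectives, PFS-4 is a further listed efficacy endpoint, and SAP section 5 tests no hypothesis. ORR does not use these rules, and neither does the Phase 2 decision, which rested on response and had already been made. It would be wrong to infer that a trial conclusion is at risk.

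In the illustration one subject moves PFS-6 by about 1 percentage point under the plain text of 10.7.3, and by 3.3 points only if the toxicity row is allowed to override a later progression. Both lie well inside the 1.7% to 40.5% interval. Where the estimate changes, the censoring reading gives the higher value. These figures rest on assumed event times and one affected subject; how many real subjects fall in each row is unknown.

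**What to change.** 1. In 10.7.3, restrict censoring at treatment start to subjects with no post-baseline assessment and no later qualifying progression or death.
2. In 12.3, restrict the toxicity/other-reason row to subjects with no later documented progression or death.
3. Date every death event at the date of death. Keep treatment end only for progression stops before the first scan, and carry that rule into the table so that it is not lost.
4. In the one-missed-visit row, use the date of progression or death, whichever is first.
5. State that 12.3, as corrected, takes precedence over 10.7.3.

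Optional: note that censoring undocumented progression and censoring after two or more missed visits go beyond protocol 5.4.4 as supplied, or add a sensitivity analysis under the protocol rule.

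The cost is SAP text and reprogramming of the PFS and DOR derivations. One drawback remains: protocol 4.4.1 leaves post-treatment MRIs to the investigator's discretion, so progression after a treatment stop will be coarsely dated, or missing, for some subjects.
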